9.4.2.4. Electrocardiograms

Descriptive statistics and mean change from baseline will be determined for each ECG parameter at each assessment time. Electrocardiogram results will be reviewed for clinically notable abnormalities according to predefined criteria ([Table 16](#)). Subjects exhibiting clinically notable ECG abnormalities will be listed.

Table 16: Criteria for Clinically Notable Electrocardiogram Abnormalities

[figure not shown]
[figure not shown]
Parameter	High Threshold	Low Threshold
QTcF	> 460 msec	< 295 msec
PR	> 220 msec	< 75 msec
QRS	> 120 msec	< 50 msec
QT	> 500 msec	< 300 msec
RR	> 1330 msec	< 600 msec

QTcF = Fridericia correction.

9.4.3. Pharmacokinetic Analysis

The PK parameters of C_{max} , T_{max} , C_{min} , and AUC_{0-t} (INCAGN01949) will be summarized by part, dose, and study cycle. The log-transformed PK parameters will be compared among dose levels by using a 1-factor analysis of variance. Dose-dependent parameters (C_{max} and AUC) will be normalized to the lowest common dose before statistical comparisons. Additionally, if sufficient data are available, then the dose proportionality of INCAGN01949 C_{max} and AUC will be evaluated statistically by using a power model (eg, $AUC = \alpha \cdot [dose^\beta]$) or equivalently $\log(AUC) = \log(\alpha) + \beta \cdot \log(dose)$, where linear dose proportionality is accepted if β is not significantly different from 1).

If there is a sufficient amount of plasma concentration data from this study, then the data will be analyzed by standard population PK methods using appropriate software (eg, NONMEM).

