9.3. Level of Significance

For the primary efficacy endpoints of objective response rate, the 1-sided Type I error will be controlled at 0.05 for each individual cohort expansion. Note that this level of significance does not account for the multiple expansion cohorts. For other endpoints, confidence intervals will be reported at a 95% confidence level.

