3.3. Control of Type I Error

All statistical analyses are exploratory in nature. Unless otherwise specified, all CIs provided will be at the 95% confidence level.

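### Dose proportionality of Cmax and AUC is accepted on a non-significant slope test with no margin, and Cmin is left out of the dose normalisation that precedes the ANOVA across doses

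*Protocol*

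**What the plan says.** Protocol 9.4.3 lists four PK parameters (Cmax, Tmax, Cmin and AUC0-t) to be summarised by part, dose and cycle. It then plans two analyses across doses.

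- **ANOVA.** "The log-transformed PK parameters will be compared among dose levels by using a 1-factor analysis of variance". No parameter is excluded. The dose-dependent parameters, named in brackets as Cmax and AUC, "will be normalized to the lowest common dose before statistical comparisons". Cmin is not named.
- **Power model.** "Additionally, if sufficient data are available", the dose proportionality of Cmax and AUC "will be evaluated statistically by using a power model", "where linear dose proportionality is accepted if" the test of β against 1 is not significant.

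SAP 7.6 repeats both analyses without adding a test level, a margin, a CI criterion or a definition of sufficient data. The nearest general statements are Protocol 9.3 ("For other endpoints, confidence intervals will be reported at a 95% confidence level") and SAP 3.3 ("All statistical analyses are exploratory in nature").

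**The concern.** A test of β = 1 that fails to reject shows only that the data did not contradict proportionality. The plan turns that result into a positive conclusion. The incentive then runs the wrong way: with fewer subjects, a narrower dose range or more variable exposure, acceptance becomes easier. The cohorts were sized by the 3 + 3 rules, not for PK, so precision for β is whatever the escalation happens to give.

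Trough concentration rises with dose just as Cmax and AUC do. If Cmin enters the log-scale ANOVA unadjusted while the other two are normalised, the three tests address different hypotheses and cannot be read side by side.

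The stake is the choice of recommended dose and schedule. Protocol 4.1.1.2 and 9.2.1 base that choice on all available safety and PK results when more than one safety expansion cohort is judged safe.

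**Working it through.** The documents give no power or precision for the PK comparison, so there is no planned figure to reproduce.

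**Inputs**
- Doses 7, 20, 70, 200, 350 and 700 mg (Protocol Table 2, SAP Table 1). The 1400 mg cohort is optional in the protocol and is not used here.
- 3 to 6 evaluable subjects per cohort (Protocol 9.2.1).
- Test level not stated. Assumed two-sided 0.05.
- Between-subject CV not stated. Assumed 30%, 40% and 50%.
- Escalation subjects only, one value each.

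**Precision of β**
- Log-scale SD: σ = √ln(1 + CV²) = 0.294, 0.385, 0.472.
- Spread of log dose: Σ(ln d − mean)² = 15.54 over the six doses, so Sxx = 46.6 with 3 per dose and 93.2 with 6 per dose.
- SE(β) = σ/√Sxx. Degrees of freedom are N − 2 = 16 or 34, with critical t = 2.120 or 2.032.

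**Departure examined**
- The fold departure over a dose ratio r is r^|β−1|. For r = 100, a 2-fold departure is |β−1| = ln 2/ln 100 = 0.693/4.605 = 0.151.
- P(accept) is the probability that a noncentral t with noncentrality 0.1505/SE falls inside the critical limits.

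| Per dose | CV | SE(β) | Noncentrality | P(accept) at a 2-fold departure |
|---|---|---|---|---|
| 3 | 30% | 0.043 | 3.50 | 9% |
| 3 | 40% | 0.056 | 2.67 | 29% |
| 3 | 50% | 0.069 | 2.18 | 47% |
| 6 | 30% | 0.030 | 4.95 | 0.2% |
| 6 | 40% | 0.040 | 3.77 | 4% |
| 6 | 50% | 0.049 | 3.08 | 15% |

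When β is exactly 1, the rule accepts 95% of the time by construction.

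**Larger departure, full range.** A slope of 0.8 (100^0.2 = 2.5-fold) with 3 per dose is accepted 1% of the time at CV 30% and 23% at CV 50%.

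**Few, adjacent doses**
- For 200, 350 and 700 mg with 3 each, Sxx = 3 × 0.788 = 2.36 and df = 7. A slope of 0.8 is accepted 85% of the time at CV 30% and 91% at CV 50%.
- That slope is only 3.5^0.2 = 1.28-fold over this narrower range. For a like-for-like comparison, a 2-fold departure over 200 to 700 mg is |β−1| = 0.693/1.253 = 0.553. With SE = 0.191, 0.251 and 0.307, it is accepted about 30%, 52% and 66% of the time at CV 30%, 40% and 50%.
- For 350 and 700 mg only, a slope of 0.8 is accepted 93% to 95% of the time (CV 30% to 80%).

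**Cmin without normalisation**
- Under exact proportionality, log Cmin at 700 mg and at 7 mg differ by ln 100 = 4.6, against an SD of about 0.39 at CV 40%.
- The ANOVA noncentrality with 3 per dose is Sxx/σ² = 46.6/0.385² ≈ 314. Even at CV 100% (σ² = ln 2) it is 46.6/0.693 ≈ 67, and the test rejects equality more than 99.9% of the time.
- For 7, 20 and 70 mg with 3 each, it rejects 79% of the time at CV 80% and almost always at CV 30%.
- A normalised comparison would reject 5% of the time under the same proportional PK.

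**The case against.** The strongest reply is that the planned dose range protects the test. A 100-fold range pooled in one regression is informative even with small cohorts, and 3 per dose is a minimum: Protocol 4.1.1.1 requires at least 3 more subjects at the MTD or PAD before Part 2 if only 3 were treated there. This stands. A reader might infer that small cohorts establish proportionality by default, and the figures do not support that for the full set of doses, where a slope off by 0.2 is usually detected at CV 30% to 50%. The description comes close to true only for small departures, high variability, or two or three adjacent doses. The unquantified condition on sufficient data is a weak guard against those cases.

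A reader might also call the Cmin comparison meaningless. It is not: it validly tests whether troughs differ between doses. It is uninformative about proportionality, and since Cmin is not in the power model, no proportionality claim rests on it.

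Nor does fixed dosing depend on this rule. Protocol 1.3.1 justifies it by convenience, fewer preparation errors, less waste and similar exposure variability.

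Finally, a change in clearance with dose could still show in the normalised Cmax and AUC comparisons, the summaries by dose, or the population PK analysis planned if data suffice. That limits the consequence. It does not justify an accept verdict based on non-significance.

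**Conclusion.** The point holds in both parts. The acceptance rule treats non-rejection as proof and sets no standard for how large a departure would matter. At the minimum cohort size, a 2-fold departure over 7 to 700 mg would pass about 9% to 47% of the time across the CVs tried. At 6 per dose it would pass about 0.2% to 15% of the time. The chance is higher if only a few adjacent doses contribute. These percentages rest on an assumed CV, an assumed two-sided 0.05 level and escalation data alone, so they are a range, not figures from the plan.

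The Cmin omission makes that test a check that the doses differ. This takes the bracketed list of Cmax and AUC as complete, which is its natural reading.

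The consequence is modest. PK is a secondary objective, the SAP calls all analyses exploratory, and PK informs the recommended dose and schedule without any decision being formally tied to this test.

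**What to change.** In Protocol 9.4.3 and SAP 7.6:

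1. Delete the rule that accepts proportionality on a non-significant β.
2. Report β for Cmax and AUC with its 90% CI, the dose range actually tested, and the implied fold departure over that range, r^|β−1|, at the estimate and at the confidence limits.
3. Claim proportionality only if the 90% CI lies within a margin that the sponsor prespecifies for the dose ratio. Otherwise report the result as inconclusive. If no margin can be justified, report β and its CI without a verdict.
4. Add Cmin to the dose-normalised parameters, or keep it descriptive and out of the ANOVA.

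This is a wording change with no effect on conduct, sampling or sample size. The cost is that the result may be inconclusive, and how often depends on the margin. Neither margin below comes from the documents.

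- **2-fold margin** (β within 0.85 to 1.15 for 7 to 700 mg): a truly proportional drug would meet it about 91%, 64% or 35% of the time with 3 per dose (CV 30%, 40%, 50%), and more than 99%, 96% or 83% with 6 per dose.
- **0.8 to 1.25 margin** on the exposure ratio (β within 0.952 to 1.048): the expected 90% half-width is already 0.075 with 3 per dose at CV 30%, so the margin would not be expected to be met.

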9.5. Analyses for the Data Monitoring Committee

Not applicable.

9.6. Interim Analysis

Part 1 of the study will use a standard 3 + 3 dose-escalation design. Each Part 1 safety expansion cohort will enroll up to 9 additional evaluable subjects. If < 3 of 9 additional evaluable subjects has a DLT, then the cohort will be deemed safe. If more than 1 safety expansion cohort is deemed safe, then a recommended dose and schedule will be determined in conjunction with the investigators and sponsor based on all available safety, PK, [REDACTED] results. The probability of declaring a dose cohort as safe for various DLT rates in the 3 + 3 and the safety expansion is summarized in [Table 17](#).

Table 17: Probability of Dose Escalation by DLT Rate for 3 + 3 Design and Safety Expansion

True DLT Rate	Probability of Declaring Dose Cohort as Safe	
	3 + 3 Design	In BOTH 3 + 3 Design and Safety Expansion
10%	90.6%	85.8%
20%	70.9%	52.3%
30%	49.4%	22.9%
40%	30.9%	7.2%
50%	17.2%	1.5%
60%	8.2%	0.2%

In Part 2, the Simon 2-stage design will be applied. During Stage 1, 9 subjects will be enrolled, and if no responses are observed, then the cohort will be discontinued. The probability of early termination for Stage 1 is summarized in [Table 18](#). If at least 1 response is observed, then 8 additional subjects will be enrolled (Stage 2).

Table 18: Probability of Early Termination at Stage 1 for Simon 2-Stage Design

True Response Rate	Probability of Early Termination at Stage 1
15%	23.2%
20%	13.4%
25%	7.5%
30%	4.0%
35%	2.1%

Subjects will continue to receive INCAGN01949 until Protocol-defined withdrawal criteria are met. Continuous evaluation of toxicity events will be performed throughout enrollment in Part 2 of the study. If the cumulative incidence of DLTs occurs in $\geq 33\%$ of subjects after 6 subjects have been observed for at least 28 days, further enrollment may be interrupted until the sponsor has determined the appropriate course of action. All AEs, regardless of the time of occurrence on study may be considered in determination of the appropriate dose, schedule, and MNTD.

Toxicity will continue to be monitored throughout the treatment period. If $> 33\%$ of subjects (minimum of 6 subjects) experience a Grade ≥ 3 toxicity related to study drug after completing ≥ 4 cycles, then dose administration will be stopped, and the MNTD will be determined in conjunction with the investigators and sponsor based on all available safety data.

10. ETHICAL CONSIDERATIONS AND ADMINISTRATIVE PROCEDURES

10.1. Investigator Responsibilities

This study will be performed in accordance with ethical principles that originate in the Declaration of Helsinki and conducted in adherence to the study Protocol; GCPs as defined in Title 21 of the US CFR Parts 11, 50, 54, 56, and 312; ICH E6 GCP consolidated guidelines; and local regulatory requirements as applicable to the study locations.

The investigator will be responsible for:

- Permitting study-related monitoring, sponsor audits, IRB/IEC review, and regulatory inspections by providing direct access to source data and other relevant clinical study documents.
 - Monitoring: Qualified representatives of the sponsor or its designee, study monitors, will monitor the study according to a predetermined plan. The investigator must allow the study monitors to review any study materials and subject records at each monitoring visit.
 - Auditing: Qualified representatives of the sponsor or its designee may audit the clinical study site and study data to evaluate compliance with the Protocol, applicable local clinical study regulations, and overall study conduct. The investigator must allow the auditors to review original source records and study documentation for all subjects.
 - Regulatory inspection: Regulatory authorities may conduct an inspection of the study and the site at any time during the development of an investigational product. The investigator and staff are expected to cooperate with the inspectors and allow access to all source documents supporting the eCRFs and other study-related documents. The investigator must immediately notify the sponsor when contacted by any regulatory authority for the purposes of conducting an inspection.
- Obtaining informed consent and ensuring that the study subjects' questions have been answered and the subjects fully understand study procedures:
 - Informed consent must be obtained before any study-related procedures are conducted, unless otherwise specified by the Protocol.
 - Informed consent must be obtained using the IRB/IEC-approved version in a language that is native and understandable to the subject. A template will be provided by the sponsor or its designee. The sponsor or its designee must review and acknowledge the site-specific changes to the ICF template. The ICF must include a statement that the sponsor or its designee and regulatory authorities have direct access to subject records.

- Obtaining approval from the IRB/IEC before the start of the study and for any changes to the clinical study Protocol, important Protocol deviations, routine updates, and safety information in accordance with institutional requirements and local law.
 - The investigator is responsible for ensuring that the safety reports provided by the sponsor are reviewed and processed in accordance with regulatory requirements and with the policies and procedures established by the IRB/IEC.
- Adhering to the Protocol as described in this document and agreeing that changes to the Protocol procedures, with the exception of medical emergencies, must be discussed and approved, first, by the sponsor or its designee and, second, by the IRB/IEC. Each investigator is responsible for enrolling subjects who have met the specified eligibility criteria.
- Retaining records in accordance with all local, national, and regulatory laws, but for a minimum period of at least 2 years after the last marketing application approval in an ICH region and until there are no pending or contemplated marketing applications in an ICH region, or if not approved, 2 years after the termination of the test article for investigation to ensure the availability of study documentation should it become necessary for the sponsor or a regulatory authority to review.
 - The investigator must not destroy any records associated with the study without receiving approval from the sponsor. The investigator must notify the sponsor or its designee in the event of accidental loss or destruction of any study records. If the investigator leaves the institution where the study was conducted, the sponsor or its designee must be contacted to arrange alternative record storage options.
 - All eCRF data entered by the site (including audit trail), as well as computer hardware and software (for accessing the data), will be maintained or made available at the site in compliance with applicable record retention regulations. The sponsor will retain the original eCRF data and audit trail.

10.2. Accountability, Handling, and Disposal of Study Drug

The investigator is responsible for drug accountability at the study site; however, some of the drug accountability duties may be assigned to an appropriate pharmacist or other designee. Inventory and accountability records must be maintained and readily available for inspection by the study monitor and are open to inspection at any time by any applicable regulatory authorities. The investigator or designee must maintain records that document:

- Delivery of study drug to the study site.
- Inventory of study drug at the site.
- Subject use of the study drug including pill or unit counts from each supply dispensed.
- Return of study drug to the investigator or designee by subjects.

The investigational product must be used only in accordance with the Protocol. The investigator will also maintain records adequately documenting that the subjects were provided the specified

study drug. These records should include dates, quantities, and any available batch or serial numbers or unique code numbers assigned to the investigational product and study subjects.

Completed accountability records will be archived by the site. The investigator or designee will be expected to collect and retain all used, unused, and partially used containers of study drug until verified by the study monitor (unless otherwise agreed to by the sponsor). At the conclusion of the study, the investigator or designee will oversee shipment of any remaining study drug back to the sponsor or its designee for destruction according to institutional standard operating procedures. If local procedures mandate on-site destruction of investigational supply, the site should (where local procedures allow) maintain the investigational supply until the study monitor inspects the accountability records in order to evaluate compliance and accuracy of accountability by the investigative site. At sites where the study drug is destroyed before monitor inspection, the monitors rely on documentation of destruction per the site SOP.

10.3. Data Management

Data management will be performed in a validated database via an Electronic Data Capture (EDC) system. All data entry, verification, and validation will be performed in accordance with the current standard operating procedures of the Data Management Department at the sponsor or its designee. The database will be authorized for lock once all defined procedures are completed.

The investigator will be provided with access to an EDC system so that an eCRF can be completed for each subject. Entries made in the eCRF must be verifiable against source documents; if updates to the database are not possible, any discrepancies should be explained and documented. The investigator will be responsible for reviewing all data and eCRF entries, and will sign and date the designated forms in each subject's eCRF, verifying that the information is true and correct. The investigator is responsible for the review and approval of all query responses.

Protocol deviations will be identified and recorded in the Protocol Deviation form of the eCRF. The study monitor will reference the Monitoring Plan in order to ensure that each issue identified is appropriately documented, reported, and resolved in a timely manner in accordance with the plan's requirements.

10.4. Data Privacy and Confidentiality of Study Records

The investigator and the sponsor or its designee must adhere to applicable data privacy laws and regulations. The investigator and the sponsor or its designee are responsible for ensuring that sensitive information is handled in accordance with local requirements (eg, HIPAA). Appropriate consent and authorizations for use and disclosure and/or transfer (if applicable) of protected information must be obtained.

Subject names will not be supplied to the sponsor or its designee, if applicable. Only the subject number and subject's initials (subject's initials will only be recorded if allowable by local regulations) will be recorded in the eCRF, where permitted; if the subject's name appears on any other document (eg, laboratory report), it must be obliterated on the copy of the document to be supplied to the sponsor or its designee. Study findings stored on a computer will be stored in accordance with local data protection laws. The subjects will be informed that representatives of the sponsor or its designee, IRB or IEC, or regulatory authorities may inspect their medical

records to verify the information collected, and that all personal information made available for inspection will be handled in strictest confidence and in accordance with local data protection laws.

10.5. Financial Disclosure

Before study initiation, all clinical investigators participating in clinical studies subject to FDA Regulation Title 21 Code of Federal Regulations (CFR) Part 54 – Financial Disclosure by Clinical Investigators (ie, "covered studies") are required to submit a completed Clinical Investigator Financial Disclosure form that sufficiently details any financial interests and arrangements that apply. For the purpose of this regulation, "clinical investigator" is defined as any investigator or subinvestigator who is directly involved in the treatment or evaluation of research subjects, including the spouse and each dependent child of the clinical investigator or subinvestigator. These requirements apply to both US and foreign clinical investigators conducting covered clinical studies.

Any new clinical investigators added to the covered clinical study during its conduct must also submit a completed Investigator Financial Disclosure Form. During a covered clinical study, any changes to the financial information previously reported by a clinical investigator must be reported to the sponsor or its designee. At the conclusion of the covered clinical study, the clinical investigators will be reminded of their obligations. In the event that the clinical investigator is not reminded, they nevertheless will remain obligated to report to the sponsor or its designee any changes to the financial information previously reported, as well as any changes in their financial information for a period of 1 year after completion of the covered clinical study.

10.6. Publication Policy

By signing the study Protocol, the investigator and his or her institution agree that the results of the study may be used by the sponsor, Incyte Biosciences International Sàrl (Incyte), for the purposes of national and international registration, publication, and information for medical and pharmaceutical professionals. Study results will be published in accordance with applicable local and national regulations. If necessary, the authorities will be notified of the investigator's name, address, qualifications, and extent of involvement. The terms regarding the publication of study results are contained in the agreement signed with the sponsor or its designee. A signed agreement will be retained by the sponsor or its designee.

